### 11.5.2 Duration of Response

Response will be defined as evidence of CR, PR, or stable disease. The duration of response will be measured from the start of treatment until the criteria for progression are met.

Duration of CR or PR: The duration of CR or PR will be recorded from the time measurement criteria are met for CR or PR (whichever is first recorded) until the first date that current or progressive disease is objectively documented (taking as reference for progressive disease the smallest measurements recorded since the treatment started).

Duration of Stable Disease: Stable disease is measured from the start of the treatment and must be at least 6 months in duration or until the criteria for progression are met,

taking as reference the smallest measurements recorded since the treatment started.

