## 11. MEASUREMENT OF EFFECT

### 11.1 Antitumor Effect-Solid Tumors

For the purposes of this study, patients should be re-evaluated for response 6 months after the initial treatment, 12 months after treatment, and at 6 month intervals thereafter.

Response and progression will be evaluated in this study using the new international criteria proposed by the Response Evaluation Criteria in Solid Tumors (RECIST 1.1) Committee (30). Changes in only the largest diameter (unidimensional measurement) of the tumor lesions are used in the RECIST criteria.

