### 11.2 Definitions

Evaluable Population: will consist of all patients who have received 1 cycle of CBI treatment preceding SBRT.

Safety Population: Will consist of all subjects who were enrolled and have received CBI combined with SBRT. This will be used to assess the clinical safety and tolerability of the study.

Evaluable for Objective Response: Only those patients who have measurable disease present at baseline, have completed all fractions of SBRT, and have had their disease re-evaluated will be considered evaluable for response. These patients will have their response classified according to the definitions stated below.

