## 11.5 Response Criteria (via RECIST 1.1)

### 11.5.1 Evaluation of Target Lesions

Complete Response (CR): Disappearance of targeted lesion.

Objective Response (OR): At least a 30% decrease in the sum of the longest diameter (LD) of targeted lesion.

Progressive Disease (PD): At least a 20% increase in the sum of the LD of Targeted lesion.

Stable Disease (SD): Neither sufficient shrinkage to qualify for PR nor sufficient increase to qualify for PD, taking as reference the smallest sum LD since the treatment started

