### **15.7 Evaluation of Response**

All patients included in the study must be assessed for response to treatment, even if there are major protocol treatment deviations or if they are ineligible. Each patient will be assigned one of the following categories: 1) complete response, 2) partial response, 3) stable disease, 4) progressive disease, 5) early death from malignant disease, 6) early death from toxicity, 7) early death because of other cause, or 8) unknown (not assessable, insufficient data).

All of the patients who met the eligibility criteria (with the possible exception of those who received no study medication) should be included in the main analysis of the response rate. Patients in response categories 4-8 should be considered to have a treatment failure (disease progression).

All conclusions should be based on all eligible patients. Sub-analyses may then be performed on the basis of a subset of patients, excluding those for whom major protocol deviations have been identified (e.g., early death due to other reasons, early discontinuation of treatment, major protocol violations, etc.). However, these sub-analyses may not serve as the basis for drawing conclusions concerning treatment efficacy, and the reasons for excluding patients from the analysis should be clearly reported. The reason for performing subset analyses would be to generate hypotheses for future prospective clinical trials.

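### Section 11.5.2 counts stable disease as response and gives CR/PR two start dates for duration, and Sections 15.5 and 15.7 do not say which rule applies

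*Combined protocol and SAP*

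**What the plan says.** All references are to the combined protocol and SAP.

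- **11.5.2, general paragraph.** "Response will be defined as evidence of CR, PR, or stable disease", followed by "The duration of response will be measured from the start of treatment until the criteria for progression are met".
- **11.5.2, CR/PR paragraph.** "The duration of CR or PR will be recorded from the time measurement criteria are met for CR or PR", taking the earlier of the two.
- **11.5.2, SD paragraph.** "Stable disease is measured from the start of the treatment and must be at least 6 months in duration". The sentence then offers progression as an alternative endpoint, which leaves the 6-month minimum unclear.
- **11.5.1.** "Objective Response (OR): At least a 30% decrease in the sum of the longest diameter (LD) of targeted lesion". SD is a separate category. PR is used in the SD definition but is never itself defined; the 30% criterion carries the label OR.
- **11.1.** "patients should be re-evaluated for response 6 months after the initial treatment", then at 12 months and every 6 months. The study calendar in Section 10 likewise schedules no RECIST measurement between baseline and 6 months.
- **15.5.** Kaplan-Meier and hazard summaries are planned for several endpoints. Duration of response and SD appear as separate items, with no reference back to 11.5.2.
- **15.7.** Each patient is placed in one of eight categories: CR, PR, SD, PD, three kinds of early death, and unknown. All eligible patients enter the main response-rate analysis, with a possible exception for those given no study drug. "Patients in response categories 4-8 should be considered to have a treatment failure (disease progression"). The numerator of the response rate is not defined.
- **11.2.** For the objective-response set, only patients with measurable baseline disease who finished SBRT and "have had their disease re-evaluated will be considered evaluable for response".

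**The concern.** Two adjacent paragraphs of 11.5.2 start the clock for the same CR or PR at different dates, and the section's definition of response is wider than the objective response of 11.5.1. Both are written rules, so an analyst could follow either and claim to be following the protocol. Because 15.5 and 15.7 do not choose, the choice could be made after the data are seen.

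Two things are at stake. Starting at treatment credits every responder with the interval before response was documented, during which a responder could not by definition have progressed. And where the only lesion has been given definitive SBRT, lack of growth is what radiation alone is expected to produce. A response rate that includes SD would therefore say little about avelumab in a single-arm study.

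**Working it through.** The plan gives no target, null value, sample size or power for response rate or duration, so there is no planned figure to reproduce. The check sets the rules side by side and sizes the gaps.

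**1. The rules compared**

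| Place | What counts as response | Start of duration |
|---|---|---|
| 11.5.2, general paragraph | CR, PR or SD | start of treatment |
| 11.5.2, CR/PR paragraph | CR or PR | criteria first met |
| 11.5.2, SD paragraph | SD, treated separately | start of treatment |
| 11.5.1 | decrease of 30% or more; SD separate | not stated |
| 15.5 | not stated | not stated |
| 15.7 | not stated; SD is not a failure | not applicable |

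**2. Duration**

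Let R be the month in which CR or PR is first recorded and P the month of progression, both from start of treatment.

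- General paragraph: duration = P.
- CR/PR paragraph: duration = P − R.
- Difference: P − (P − R) = R.

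The earliest scheduled RECIST assessment after baseline gives R = 6 (11.1).

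| P (months) | From start of treatment | From first documentation |
|---|---|---|
| 12 | 12 | 12 − 6 = 6 |
| 24 | 24 | 24 − 6 = 18 |
| 36 | 36 | 36 − 6 = 30 |

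Section 6.4 also lists chest CT at 6 weeks and 3 months. If a response were dated from the 3-month scan, the difference would be about 3 months. No RECIST reading is scheduled then, so about 6 months is the planned case for a response recorded at the first assessment.

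**3. Numerator**

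The documents give no response rate for SBRT plus avelumab in Stage I disease. Two of their figures show only how much SD can matter.

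- Avelumab study described in 4.2 (advanced, previously treated NSCLC, avelumab alone): CR+PR = 22/184 = 12.0%. The exact 95% interval recomputes to 7.6% to 17.5%, matching the interval printed there. SD = 70/184 = 38.0%. CR+PR+SD = (22 + 70)/184 = 92/184 = 50.0%, and 92/22 = 4.2-fold.
- Section 4.1 quotes local control above 90% with SBRT alone. If that is taken as a proxy for no progression of the treated lesion (an assumption), CR+PR+SD on that lesion could be near 90% without any drug effect.

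**4. Denominator**

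If 11.2 were used in place of 15.7, a rate with N = 56 and k patients not evaluable would rise by the factor 56/(56 − k). The value of k is assumed; the 10% dropout in 15.2 gives 5.6, rounded to 6.

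| k | Factor |
|---|---|
| 3 | 56/53 = 1.06 |
| 6 | 56/50 = 1.12 |
| 8 | 56/48 = 1.17 |
| 11 | 56/45 = 1.24 |

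This arises only if 15.7 is set aside, and 15.7 claims the main analysis for its own set.

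**The case against.** The best defence is that the pieces of a sound definition are already present. Section 11.5.2 has its own paragraph for CR/PR, dated from documentation, and another for SD. Sections 11.5.1, 15.5 and 15.7 all list SD separately. The broad sentence sits under a heading about duration and never mentions a rate. A careful analyst could treat the specific paragraphs as overriding the general one.

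That reading is reasonable, but nothing in the text requires it. The general paragraph is a complete rule with its own start date, and 15.5 names duration of response, the very term that paragraph defines. Even the charitable reading leaves one curve that could mix patients timed from treatment (SD) with patients timed from documentation (CR/PR).

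Other parts of the defence stand in full:

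- **Denominator.** A reader might infer from 11.2 that early deaths and unassessable patients drop out of the response rate. The documents do not support this. Section 15.7 makes all eligible patients the main set, counts categories 4 to 8 as failures, and bars efficacy conclusions from subsets. Section 11.2 says whose response is classified and does not mention a rate. The 10% dropout is also not stated to fall before the first assessment.
- **Importance.** Response rate and duration of response are not among the objectives in Section 3 and carry no hypothesis or sample size. RFS is defined in 11.5.3 without reference to CR, PR or SD.
- **Transferability.** The 12.0% and 50.0% come from a different disease setting without SBRT and cannot forecast this trial.

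**Conclusion.** The point holds as a contradiction between stated rules, not merely a missing detail. Section 11.5.2 gives two start dates for a CR or PR and a response definition that 11.5.1 does not share, and neither 15.5 nor 15.7 settles them.

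For duration, the two rules differ by the time to first documentation. That is about 6 months for a CR or PR first recorded at the 6-month RECIST assessment, for example 24 against 18 months with progression at month 24. The figure assumes responses are dated from scheduled RECIST assessments and shrinks if earlier scans are used. For the response rate, the direction is certain, since adding SD cannot lower it, but the size in this population cannot be derived from the documents.

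A reader might go further and infer that the trial's efficacy result will be materially inflated. The documents do not support that: these are descriptive summaries, and the Phase II conclusion rests on RFS, which is untouched. This is a minor point, worth correcting because the correction is cheap.

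**What to change.** - **11.5.2:** define response as CR or PR and measure its duration from the first documented CR or PR. Report SD separately, or report CR+PR+SD under the name disease control. Remove the general start-of-treatment rule for response.
- **11.5.1:** label the 30% criterion PR, so that objective response means CR or PR throughout.
- **15.5 and 15.7:** add one line each saying that these definitions apply, including that SD is not in the response-rate numerator.
- **11.2:** add one line saying that the objective-response-evaluable set is a sensitivity analysis to the all-eligible analysis in 15.7. The definition itself can stay.

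The cost is a few lines of amendment, with no new patients, visits or data. The reported response rate may be lower and the duration shorter than under the general paragraph, but both will be interpretable. Sample size and the RFS analysis do not change.

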### **11.5.3 Clinical Response Parameters**

**Time to Local Progression (TTLP)** is defined as the elapsed time from the start of treatment to the date of documented local progression or death, whichever happens earliest.

**Relapse-Free Survival (RFS)** is defined as the time from starting treatment to the time of first documented tumor progression or death due to any cause, whichever occurs first. Death is considered as an event here. For subjects whose disease does not progress or who do not die, PFS will be censored at the time of the last visit.

**Time to Progression (TTP)** is defined as the time from starting treatment to the time of first documented tumor progression. Subjects who do not progress will be censored at the time of the last contact. In addition, death from any cause will also be censored.

**Overall Survival (OS)** is defined as the time from starting treatment until death due to any cause. For subjects who do not die, time to death will be censored at the time of last contact.

**Locoregional Control (LRC)** is defined as the time from starting treatment until local and/or regional relapse is documented

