#### 6.4 Follow-Up Procedures

Subsequent to SBRT, patients will be followed clinically, radiographically, and with bloodwork. A detailed medical and physical examination will be performed at 4 weeks, 8 weeks, and 16 weeks, 6 months, 12 months, 18 months, 24 months, 30 months, and 36 months. A complete blood count (CBC) and comprehensive chemistry panel and CT Chest with contrast will be performed at 6 weeks and 3 months and will continue at intervals of every 6 months until 2 years post SBRT treatment.

Recist 1.1 measurements at 6 months and 1 year and 2 years will be used to determine radiographic response for loco-regional control and relapse free survival.

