#### 6.7 Criteria for Removal of Subjects from Study Treatment and Study

- Unacceptable adverse events grade IV or greater with an attribution of possibly related while on CBI or after SBRT.
  - Subject withdraws consent for follow-up;
  - Subject is lost to follow-up;
  - Subject dies;
  - Study is terminated for any reason.
- ξ The patient has a confirmed positive serum pregnancy test;

ξ General or specific changes in the patient's condition render the patient unacceptable for further treatment in the judgment of the investigator;

ξ Administrative Decision

Subject can elect to discontinue treatment at any time. If participants withdraw from the study, they will be followed for survival data.

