## **15. STATISTICAL CONSIDERATIONS**

### **15.1 Endpoints**

#### **15.1.1 Primary Objectives**

Phase I: The Phase I primary endpoint is safety and tolerability as described in Section 3.1.1. Tolerability and safety of will be determined after all patients have completed six doses or have discontinued dosing prior to completing six doses. Safety analyses will be performed in all treated subjects. Descriptive statistics of safety will be presented using National Cancer Institute (NCI) Common Terminology Criteria for Adverse Events (CTCAE) version 4.0.

Phase II: The Phase II primary endpoint is to determine the relapse free survival rate at a median followup of 2 years in early stage NSCLC treated with definitive SBRT combined with 6 cycles of concurrent and adjuvant Avelumab.

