#### **15.2 Sample Size/Accrual Rate**

Phase I: The purpose of the Phase I part of this study is to evaluate the tolerability and safety profile SBRT combined with concurrent and adjuvant Avelumab at 10mg/kg. For this purpose, 12 subjects will be enrolled. Although the sample sizes are not based on statistical power considerations, data from these subjects will provide toxicity and dosing information on administration Avelumab in combination with SBRT in patients with early Stage NSCLC. The accrual rate is estimated at 3 patients per month.

Phase II: The primary endpoint will be relapse free survival (RFS) rate at median followup of 2 years. The accrual rate is estimated at 3 patients per month, and the patients will be

followed for up to 3 years. A total of 56 patients will be entered in the study accounting for a 10% dropout rate. This study would have 80% power to detect a 10% absolute improvement in RFS at 2 years from 80% to 90% using a one-sided t-test at significance level 0.10. RFS estimate at 2 years was based upon analysis of relevant literature[55-57].

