### 15.4 Analysis of Primary Objectives

Phase I: If no more than one-third of the subjects permanently discontinue study medication prior to completing six doses due to treatment related adverse events then this combination will be deemed as tolerable and return to the IRB, DMC, and Sponsor for further evaluation and approval prior to proceeding to the Phase II cohort.

If  $\geq 4$  patients in the Phase I cohort permanently discontinue study medication prior to completing six doses due to treatment related adverse events then we will suspend the study and return the study to the IRB and DSMB committees for further evaluation and recommendations.

Phase II: The primary efficacy analysis will be the relapse free survival (RFS) rate in patients with early Stage NSCLC receiving SBRT combined with concurrent and adjuvant Avelumab compared to SBRT alone historical controls. The analysis population includes all registered subjects who have received SBRT and at least 2 cycles of Avelumab.

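### RFS is censored at the last visit although relapse is read mainly from scans, so 2-year RFS can be overstated against the fixed 80% if patients keep attending after scans stop

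*Combined protocol and SAP*

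**What the plan says.** Section 11.5.3 counts progression and death from any cause as RFS events. For patients with neither, it says: "For subjects whose disease does not progress or who do not die, PFS will be censored at the time of the last visit". The sentence sits inside the RFS definition but names PFS. For time to progression (TTP) the date is different: "Subjects who do not progress will be censored at the time of the last contact". No other section replaces either rule or says how missed scans are handled.

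The source of relapse information is imaging. Section 6.4 says "Recist 1.1 measurements at 6 months and 1 year and 2 years will be used to determine radiographic response" and names locoregional control and RFS as the outcomes so determined. Sections 11.1 and 11.5 evaluate progression by RECIST 1.1.

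The endpoint carries the Phase II conclusion. Section 15.1.1 aims to "determine the relapse free survival rate at a median followup of 2 years", and Section 15.2 claims "80% power to detect a 10% absolute improvement in RFS at 2 years from 80% to 90% using a one-sided t-test at significance level 0.10". Section 15.4 makes the comparison in patients "receiving SBRT combined with concurrent and adjuvant Avelumab compared to SBRT alone historical controls". Kaplan-Meier estimation is named only in Section 15.5, under the secondary objectives.

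**The concern.** A clinic visit without a scan is weak evidence that there has been no relapse, yet the rule counts it as full evidence. A patient scanned at 12 months and seen at 24 stays in the risk set for the whole second year as relapse-free, while patients who are still scanned have their relapses found. That adds to the Kaplan-Meier denominator without adding events, and pushes the estimate up.

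Missed scans are plausible here: patients are inoperable or refuse surgery, and ECOG 2 is allowed. The trial has no concurrent control arm in which the same distortion would appear. Any upward bias goes directly into the comparison with 80%, at a one-sided 0.10 level.

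**Working it through.** **1. The plan's own figures.** The test sets 80% against 90% at 2 years, and "A total of 56 patients will be entered in the study accounting for a 10% dropout rate". The arcsine formula gives n = [(1.2816 + 0.8416) / (2 × (1.2490 − 1.1071))]² ≈ 56 before any dropout. No variant tried gives 56 after dropout. That is a separate matter; 56 is used below only as the trial size.

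**2. Visits against scans.**

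| Source | Months |
|---|---|
| Examinations (6.4) | 4, 8 and 16 weeks; 6, 12, 18, 24, 30, 36 months |
| CT (6.4) | 6 weeks, 3 months, then 6-monthly to 2 years |
| RECIST (6.4) | 6, 12, 24 |
| Re-evaluation (11.1) | 6, 12, then 6-monthly |
| RECIST (calendar, as far as legible) | 6-monthly to 36 |

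For a patient who follows the schedule, visit and scan dates nearly coincide from month 6 to month 24. The exception is 6.4 read alone: a patient last seen at 18 months would be censored 6 months after the last listed RECIST read.

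**3. Bias when visits continue past month 24.** Nobody is censored before 24 months, so the Kaplan-Meier value is the proportion with no recorded event. Let d be the share who stop scans (not in the documents; assumed 10 to 30%) and A their apparent 24-month RFS. Then

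bias = d × (A − 0.80), with true S(t) = 0.8^(t/24).

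- *All first events are relapses; scans at 3, 6, 12, 18 and 24 months; stopping after 3, 6, 12 or 18 equally likely.* A = (0.9725 + 0.9457 + 0.8944 + 0.8459)/4 = 0.9146.
- *Two-thirds relapses, one-third deaths; 6-monthly scans; stopping after month m.* A = 0.8^(m/24) × 0.8^((24−m)/72). For m = 6: 0.9457 × 0.9457 = 0.8944. For m = 12: 0.8944 × 0.9635 = 0.8618.
- *One-third relapses, two-thirds deaths.* A = 0.8^(m/24) × 0.8^((24−m)/36). For m = 6: 0.9457 × 0.8944 = 0.8459. For m = 12: 0.8944 × 0.9283 = 0.8303.

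| Bias in points | d = 10% | 20% | 30% |
|---|---|---|---|
| All relapses | 1.1 | 2.3 | 3.4 |
| Two-thirds relapses | 0.6–0.9 | 1.2–1.9 | 1.9–2.8 |
| One-third relapses | 0.3–0.5 | 0.6–0.9 | 0.9–1.4 |

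**4. Shorter gaps (simulation, true RFS 80%).** With all events relapses and 10% stopping, last-visit censoring gives 80.4%, 80.7% and 81.1% when visits run 6, 12 and 24 months past the last scan, and 80.0% when the dates coincide. Now let visits end 6 months after the last scan and go on counting later deaths. At 20% stopping the result is 80.0–80.2% with two-thirds relapses, and 79.0–79.7% with one-third.

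**5. Effect on the test.** By normal approximation with n = 56, the cut-off is 0.80 + 1.2816 × √(0.8 × 0.2/56) = 0.8685. If bias moves the expected estimate to 81, 82 or 83%, the false-positive rate rises from 0.10 to 0.13, 0.17 or 0.22. An exact binomial rule (50 of 56) starts at 0.051 and gives 0.073, 0.102 and 0.139.

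**6. Check of the remedy.** Last-scan censoring returns 80.0% when all events are relapses. If deaths up to the last visit also count, it errs low. With 30 to 60% of first events deaths, it gives 79.35–79.82% at 10% stopping and 77.83–79.47% at 30%. Counting only deaths within one scan interval of the last scan gave about 78.7–79.9%.

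**The case against.** The strongest reply is that the harm depends on behaviour that the documents do not describe. Visits and scans are scheduled together for most of the period that matters, and the only attrition figure is a 10% dropout, which is not a rate of attending without scans. The larger biases need patients to attend for a year or more unscanned and relapse to be the main event. The background data point the other way on the second: one cited phase II study of inoperable patients had 3-year overall survival of 43% against cause-specific survival of 82%. Deaths are captured whether or not scans are done. All of this stands, and it makes the size conditional.

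Three further points stand:

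- The progression definition is not confined to scans, so relapse recognised clinically at a visit would reduce the bias.
- The 80% comes from literature whose censoring rules cannot be seen here. A shared convention could offset part of the bias.
- The primary estimator is not fixed. The figures above assume Kaplan-Meier at 24 months.

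The reply does not remove the defect. The rule as written credits unscanned time, and nothing else in the plan limits that.

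**Conclusion.** The censoring date is poorly chosen for an endpoint read mainly from imaging and should be changed. With visits continuing long after the last scan, the 2-year estimate can be too high by about 0.3 to 1.1 points at 10% stopping, 0.6 to 2.3 at 20% and up to about 3 at 30%. These rates, the relapse-to-death mix and the length of unscanned attendance are all assumptions. Confidence in the defect is high; confidence in its size is moderate.

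A reader might infer more than the documents support:

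- *That 2-year RFS is overstated.* It can be. With coinciding visits and scans the bias is zero.
- *That the bias can only run upward.* It is near zero or negative when visits end soon after scans and later deaths still count.
- *That patients without scans count as relapse-free indefinitely.* They leave the risk set at their last visit, and their deaths are events.
- *That visits after CT ends at 2 years inflate the result.* Those visits affect RFS only after month 24.
- *That the TTP rule harms the primary test.* TTP is neither an objective in Section 3 nor in the Section 15.5 list. Section 6.7 does say "If participants withdraw from the study, they will be followed for survival data", so survival contacts could lengthen TTP. A survival contact is not a visit, so this does not reach RFS.

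**What to change.** In 11.5.3, replace the RFS censoring sentence with: *RFS for patients without an event is censored at the date of the last evaluable tumour assessment, or at the start of treatment if there is none after baseline.* This also corrects PFS to RFS. In addition:

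- Keep death from any cause as an RFS event, and prespecify how deaths after missed scans are handled: either all count, or only those within a stated interval of the last assessment. Report the other rule as a sensitivity analysis. The one-interval rule departs from the current RFS definition, so it should not be the only analysis.
- Report last-visit censoring as a further sensitivity analysis.
- Use the same censoring date for TTP if it is reported. OS stays at last contact.
- Reconcile the RECIST time points in 6.4 with 11.1 and the calendar.

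The cost is one sentence, a stated death rule and two sensitivity analyses, with no new data. Follow-up time falls slightly, so the interval widens slightly. Counting all later deaths errs low, slightly at 10% stopping and by more if many patients stop scans and deaths dominate. That direction is conservative for a claim of improvement over 80%.

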## **4. BACKGROUND**

### **4.1 Early Stage Non-small cell Lung Cancer (NSCLC)**

Lung cancer is the number one cause of cancer related mortality in men and women in the US. The majority of patients present after they become symptomatic and are diagnosed with advanced stage disease. However, approximately 10-15% of patients present with early stage I NSCLC. Treatment is critical in these patients as Stage I-II NSCLC left untreated results in a median OS of 1 year and median 5-year OS of 10%. The primary treatment modalities for early stage lung cancer include surgical resection or definitive stereotactic body radiation therapy alone. Nevertheless, even with current standard of care SBRT in patients with early stage NSCLC the 3 year overall survival has been reported at 36-52% due to a high rate of distant metastatic disease. Thus, additional systemic therapies are critically needed in this population to decrease relapse rates and improve overall survival.

Surgical resection is indicated in patients with early stage NSCLC who are medically operable with good performance status. Definitive SBRT alone is the preferred treatment option for medically inoperable patients or those who refuse surgery. SBRT is also an appropriate option for patients with high surgical risk (able to tolerate sublobar resection but not lobectomy [eg, age  $\geq 75$  years], poor lung function). Definitive SBRT for early stage lung cancer has an excellent local control rate of greater than 90% which compares favorably with surgery[2]. However, the distant relapse free survival rate with surgery or SBRT for early Stage I NSCLC is approximately 80%, and hence approximately one out of every five patients will develop recurrent disease. Given this high failure rate there is a critical need to improve regional and distant control in the patient population. Checkpoint blockade immunotherapy targeting PD-1/PD-L1 has known activity in NSCLC and thus represents an ideal class of systemic agents to test in this patient population.

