### 15.5 Analysis of Secondary Objectives

- To determine whether SBRT combined with concurrent and adjuvant Avelumab results in improved loco-regional control, relapse free survival, and overall survival we will evaluate the recist criterion scans and survival rates at 6 months, 12 months and 24 months.
- To analyze whether SBRT combined with concurrent and adjuvant Avelumab impacts anti-tumor immune responses we will perform immunologic assays quantifying lymphocyte specificity and activation, including Immune cell Sequencing, ProtoArrays, Immunoassays, cell free DNA analyses, and multiparametric flow cytometry.
- Hazard rate estimates and 95% confidence intervals as well as Kaplan-Meier (KM) estimates will be used to summarize survival (OS), progression free survival (RFS), time to locoregional progression (TTLP) and time to distant progression (TTDP),

duration of response functions over time, and stable disease (SD). The median OS, PFS, TTLP, TTDP, and SD will be reported.

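### No planned Kaplan-Meier curve gives the proportion of patients with locoregional or distant relapse: deaths are counted as failures, censored or left without a rule; use cumulative incidence

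*Combined protocol and SAP*

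**What the plan says.** The combined protocol and SAP treats death in four ways across its progression endpoints.

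- **TTP** (section 11.5.3): "death from any cause will also be censored".
- **TTLP** (section 11.5.3): the time to "documented local progression or death, whichever happens earliest". Death is an event.
- **LRC** (section 11.5.3): "defined as the time from starting treatment until local and/or regional relapse is documented". Death is not mentioned.
- **TTDP**: listed for analysis in section 15.5 but defined nowhere.

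For relapse-free survival (RFS), the primary endpoint, section 11.5.3 is clear: "Death is considered as an event here".

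On estimation, section 15.5 says "Hazard rate estimates and 95% confidence intervals as well as Kaplan-Meier (KM) estimates will be used to summarize survival", and the list that follows includes RFS, TTLP and TTDP. There TTLP is called locoregional; in section 11.5.3 it is local only. TTP and LRC are not on that list. For locoregional control section 15.5 offers only scans and survival rates at 6, 12 and 24 months. Section 3.2.1 makes locoregional control against historical SBRT-alone controls a secondary objective. Competing risks and cumulative incidence are mentioned nowhere.

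On mortality, section 4.1 states that after SBRT the "3 year overall survival has been reported at 36-52" per cent.

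**The concern.** A patient who dies without relapse cannot relapse later. Censoring that death lets KM treat the patient as still at risk, so 1-KM answers a hypothetical question (relapse if nobody died) and is larger than the share of patients who relapse. Counting the death as an event gives a valid curve for a composite, but the curve is then driven by mortality and cannot be read as a relapse rate.

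Secondary objective 3.2.1 needs a locoregional relapse proportion that can be set beside a published one. The text lets two analysts produce very different locoregional curves from the same data, neither of them showing that proportion.

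**Working it through.** The documents give no numerical target for TTP, LRC, TTLP or TTDP, so there is no planned figure to reproduce.

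**Inputs**
- 3-year overall survival (OS) 36-52% (section 4.1).
- 3-year locoregional control 87%, so 13% failure; 3-year distant metastasis 22%; median OS 48 months (cooperative-group phase II SBRT study, section 4.3).
- Design RFS at 2 years 80% and 90% (section 15.2).
- Readouts at 6, 12 and 24 months (sections 6.4 and 15.5).

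**Case A: death counts as an event (TTLP as defined in section 11.5.3).** The composite event proportion is at least 1 - OS. At 3 years that is at least 1 - 0.52 = 48% to 1 - 0.36 = 64%, against the cited 13% for locoregional failure. No model is needed.

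**Case B: deaths censored (the TTP rule, or LRC and TTDP if handled that way).** Assume constant, independent hazards: a for the relapse type, b for death without it.
- 1-KM = 1 - exp(-a t)
- Cumulative incidence = a/(a+b) × [1 - exp(-(a+b) t)]

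Taking 13% as a 1-KM figure, a = -ln(0.87)/3 = 0.0464 per year. Treating every death as competing, b = -ln(0.52)/3 = 0.2180 or b = -ln(0.36)/3 = 0.3405 per year.

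| Locoregional failure | 1-KM | Incidence, OS 52% | Incidence, OS 36% | Gap (points) |
|---|---|---|---|---|
| 3 years | 13.0% | 9.6% | 8.2% | 3.4-4.8 |
| 2 years | 8.9% | 7.2% | 6.5% | 1.7-2.4 |

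For distant failure, a = -ln(0.78)/3 = 0.0828, and 22% by 1-KM at 3 years corresponds to 16.4% (OS 52%) or 14.1% (OS 36%).

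**Sensitivity to mortality.** The 13% and 22% come from a study with median OS 48 months. Under a constant hazard that is a 3-year OS of 0.5^0.75 = 59%, above the 36-52% range. With it, the 3-year figures are 10.2% and 17.3%, still with every death competing.

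**Under the design's own RFS.** Let 25-75% of first events be deaths. Relapse incidence at 2 years is the relapse share times (1 - RFS), and 1-KM is 1 - RFS^(relapse share). With RFS 80% and equal shares, that is 10.0% against 1 - 0.80^0.5 = 10.6%. Over all combinations the gap is 0.1-0.6 points.

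**The case against.** Much of the case on the other side is sound.

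- **TTP and LRC are not on the KM list.** This stands: that they would be estimated by KM is an inference. But LRC is defined as a time, no other time-to-event estimator is named, and TTDP is on the list with no rule for death.
- **TTLP is free of the censoring bias because death is an event.** Also true. Its fault is different: it is a composite, local in one section and locoregional in the other.
- **All-cause mortality overstates the competing risk.** Section 4.1 attributes the low survival to distant metastases, and deaths after distant relapse do not compete with distant failure or TTP. This stands for those endpoints. It carries less weight for locoregional failure, because death from distant disease without locoregional relapse does compete. The single-centre phase II study in section 4.3 reports 3-year OS 43% and cause-specific survival 82%. Under independence that implies survival from non-cancer death of 0.43/0.82 = 0.52, so non-cancer deaths alone can be numerous.
- **Three years is not the readout.** Correct, and the 2-year gap is about half as large.
- **The design's RFS makes the gap negligible.** It does if that RFS holds. RFS cannot exceed OS, however, and 3-year OS of 36-52% implies 2-year OS of about 51-65% under constant hazards (71% from a 48-month median). Low mortality cannot be taken for granted, although patients who refuse surgery may do better.

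A reader might also infer that KM distorts a comparison with a historical series of different mortality. The documents do not support this. In the model above, 1-KM stays at 13% at either OS value, while cumulative incidence moves from 9.6% to 8.2%. What matters is that both sides use the same estimator, and the protocol does not say which estimator produced the historical 87% and 22%.

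**Conclusion.** The concern holds in a limited form. As written, the plan yields no estimate of the proportion of patients with locoregional or distant relapse. TTLP as defined would show at least 48-64% with an event at 3 years if OS is 36-52%. Where deaths are censored, 1-KM is too high as a proportion. For locoregional failure the excess is at most about 3.4-4.8 points at 3 years and 1.7-2.4 points at 2 years over that OS range, and under 1 point at 2 years if the design's RFS is right. These sizes rest on constant independent hazards, on reading the cited 13% as a 1-KM figure and, for the upper bound, on treating every death as competing.

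The primary RFS analysis, the sample size and the power are not affected. Cause-specific hazards with deaths censored remain valid as hazards.

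**What to change.** 1. Reconcile TTLP between sections 11.5.3 and 15.5: local or locoregional, and with or without death as an event.
2. Define TTDP, and state in each of TTP, LRC, TTLP and TTDP how death without the event is handled.
3. Estimate locoregional, distant and any progression by the Aalen-Johansen cumulative incidence function, with death without that event as the competing event and 95% confidence intervals, reported at the planned time points.
4. For the historical comparison in objective 3.2.1, use the comparator's estimator. Where the historical figure is KM-based, show 1-KM with deaths censored beside the cumulative incidence, and label both.

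The cost is a few sentences in sections 11.5.3 and 15.5 and a few lines of code, with no new data, visits or patients. The small downside is two curves for some endpoints.
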